4.1.1 Inclusion Criteria

To be enrolled into the study, subjects must meet all of the following inclusion criteria:

1. Capable of providing written informed consent and willing and able to adhere to all protocol requirements.
2. Male and female subjects ≥ 25 years of age at the time of signing the ICF.
3. Current diagnosis of T2DM.
4. Urinary ACR ≥ 150 mg/g (16.95 mg/mmol) from a 24-hour timed urine collection.
5. Renal function: eGFR ≥ 60 mL/min/1.73m² based on central laboratory assessment using the Chronic Kidney Disease Epidemiology Collaboration (CKD-EPI) formula.
 - With approval of the IDMC, following review of safety and PK data from the first 18 subjects with preserved renal function, subjects with eGFR ≥ 45 mL/min/1.73m² can be enrolled.
 - Subsequently, after an IDMC review of safety and PK data from the first 36 subjects (at least 8 with eGFR ≥ 45 to < 60 mL/min/1.73m²) followed for at least 4 weeks, inclusion of subjects with eGFR > 20 to < 45 mL/min/1.73m² will be permitted if approved by the IDMC.

If inclusion of subjects with eGFR below 60 mL/min/1.73m² is endorsed by the IDMC, the following target sample size(s) will be established for subjects with eGFR in the specified range:

- At least 36 subjects with eGFR < 60 mL/min/1.73m²
- At least 18 subjects with eGFR < 45 mL/min/1.73m²

To achieve these targeted minimums, a restriction may be imposed on the enrollment of subjects with eGFR ≥ 60 mL/min/1.73m² and / or ≥ 45 mL/min/1.73m².

6. Glycosylated HbA1c $< 12\%$.
7. Subjects must have been taking stable doses of angiotensin-converting enzyme inhibitor (ACEi) or angiotensin II receptor blocker (ARB) therapy for at least 8 weeks before Screening. Subjects with documented intolerance to treatment with ACEi and ARB can be enrolled.
 - Subjects taking antihypertensive medication(s) must have been taking stable doses for at least 8 weeks before Screening

8. If the subject takes SGLT2 inhibitors, dose must be stable for at least 4 weeks before Screening.
 - Every effort will be made to ensure that at least 50% of randomized subjects are receiving concomitant treatment with an SGLT2 inhibitor

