10.3.7 Other Analyses

Secondary Endpoint

The number of subjects with a positive immunogenicity test at any time posttreatment will be counted and compared between treatments with Fisher's Exact Test. The comparison will be of CSL346 (8 mg/kg and 16 mg/kg pooled) versus placebo. This analysis will be performed on the Safety Analysis Set.

Exploratory Endpoints

Exploratory endpoints will employ a model similar to the primary endpoint. The analysis for these continuous endpoints is an MMRM analysis of change from Baseline to each postbaseline measurement. The model will include treatment, stratification related to the concomitant use of SGLT2 inhibitors, visit (as a categorical factor), and interactions between visit and each of the other model terms, as well as the corresponding baseline measurement as a covariate. Exploratory urinary biomarkers will be normalized to creatinine level for analysis and reporting. Treatment comparisons of interest will be similar to that of the primary endpoint. These analyses will be performed on the PD Analysis Set.

The number of subjects who regress from macroalbuminuria to microalbuminuria or normoalbuminuria, or from microalbuminuria to normoalbuminuria at Week 16 will be counted and compared between treatments using Fisher's Exact Test. The comparison will be of CSL346 (8 mg/kg and 16 mg/kg pooled) versus placebo.

11 Quality Assurance

The study may be subject to an audit by CSL, an authorized representative(s) of CSL and / or inspections by an authorized health authority (eg, US Food and Drug Administration). Health authorities may request access to all study documentation, including source documents for

inspection and copying, in keeping with local regulations. CSL will notify the Investigator of any upcoming audit / inspection.

In the event of an audit, all pertinent study-related documentation must be made available to the auditor(s). If an audit or inspection occurs, the Investigator at each study site will permit the auditor / inspector direct access to all relevant documents and allocate their time as well as the time of relevant staff to discuss the findings and any relevant issues.

12 Regulatory and Ethics Considerations

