#### 4.1.4 Exploratory Endpoints

The exploratory endpoints for this study are:

1. Changes from Baseline to each assessment in fasting values for the following PD biomarkers:
  - biomarkers of lipid metabolism including but not limited to circulating total cholesterol, triglycerides, high density lipoproteins (HDL), low density lipoproteins (LDL), glycerol, non-esterified fatty acids (NEFA), and ketones;
  - biomarkers of glycemic control including but not limited to fasting glucose and hemoglobin A1c (HbA1c);
  - novel biomarkers, including but not limited to soluble tumor necrosis factor receptor 1 (sTNFR1), and urinary VEGF-A, soluble VEGF receptor 1 (VEGF-R1), kidney injury molecule-1 (KIM-1), neutrophil gelatinase-associated lipocalin (NGAL), epidermal growth factor (EGF), clusterin, and monocyte chemoattractant protein-1 (MCP-1).
2. Concentration of CSL346 found in urine at Week 1 (Visit 5) and Week 12 (Visit 9).
3. Number (percent) of patients who regress from macroalbuminuria to microalbuminuria or normoalbuminuria, or from microalbuminuria to normoalbuminuria at Week 16 (Visit 10) compared to Baseline.

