## **5 Changes from the Protocol Planned Analyses**

The following represent changes in this SAP from the protocol:

- Definition for the Per Protocol Analysis Set has been edited in this SAP and is different from the definition provided in the protocol.
- VEGF-B analyses have been removed as the assay is not available.

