An exploratory analysis of the primary endpoint of ACR will be a categorical analysis of the number of subjects showing a gross change in albuminuria status from baseline to Week 16. As noted above, this will compare the number of subjects in each treatment group who improve from macroalbuminuria at baseline (ACR >300 mg/g [33.9 mg/mmol]) regressing to microalbuminuria (ACR >30 and ≤300 mg/g [>3.39 and ≤33.9 mg/mmol]) or normoalbuminuria (ACR ≤ 30 mg/g [3.39 mg/mmol]) OR from microalbuminuria to normoalbuminuria at Week 16. For analysis of a step change in albuminuria status (i.e., from macroalbuminuria or microalbuminuria to normal albuminuria or microalbuminuria to normal albuminuria OR from microalbuminuria to macroalbuminuria) Cochran-Mantel-Haenszel test stratified for SGLT2i will be employed to compare subjects receiving CSL346 versus placebo.

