### 16.9 Directionality of One-sided Tests

Since treatment comparisons in this study are based on one-sided tests, we need to designate the direction of these tests. Directionality and method for calculating one-sided p-value from the two-sided p-value is specified in the table below.

Parameter Name	Better (Lower or Higher)	Comment	One sided p-value calculated as:
Biomarkers of Lipid Metabolism: Total Cholesterol	Lower	Compared to PBO	estimate < 1 p-one sided=p/2 estimate >= 1 p-one sided=1-p/2
Biomarkers of Lipid Metabolism: Triglycerides –	Lower	Decreased triglycerides in the fed state, compared to PBO could indicate activity, but in fasted samples, no change would be predicted.	estimate < 1 p-one sided=p/2 estimate >= 1 p-one sided=1-p/2
Biomarkers of Lipid Metabolism: HDL –	Higher	Compared to PBO	estimate < 1 p-one sided=1-p/2 estimate >= 1 p-one sided=p/2
Biomarkers of Lipid Metabolism: LDL –	Lower	Compared to PBO	estimate < 1 p-one sided=p/2 estimate >= 1 p-one sided=1-p/2
Biomarkers of Lipid Metabolism: (Fasting) Glycerol –	Higher	Smaller (or no) increase in fasting glycerol, NEFA, ketones compared to PBO could indicate activity	estimate < 1 p-one sided=1-p/2 estimate >= 1 p-one sided=p/2
Biomarkers of Lipid Metabolism: (Fasting) NEFA –	Higher		estimate < 1 p-one sided=1-p/2 estimate >= 1 p-one sided=p/2
Biomarkers of Lipid Metabolism: (Fasting) Ketones –	Higher		estimate < 1 p-one sided=1-p/2 estimate >= 1 p-one sided=p/2
Biomarkers of VEGF Family: Urinary VEGF-A	Lower	Decrease in total VEGF-A compared to PBO could indicate activity	estimate < 0 p-one sided=p/2 estimate >= 0 p-one sided=1-p/2
Biomarkers of VEGF Family: Urinary Soluble VEGF-R1	Lower	Decrease in total VEGF-R1 compared to PBO could indicate activity	estimate < 0 p-one sided=p/2 estimate >= 0 p-one sided=1-p/2
Biomarkers of Tubular Injury: KIM-1	Lower	Compared to PBO	estimate < 0 p-one sided=p/2 estimate >= 0 p-one sided=1-p/2

Biomarkers of Tubular Injury: NGAL	Lower	Compared to PBO	estimate < 0 p-one sided=p/2 estimate >= 0 p-one sided=1-p/2
Biomarkers of Tubular Injury: MCP-1	Lower	Compared to PBO	estimate < 0 p-one sided=p/2 estimate >= 0 p-one sided=1-p/2
Biomarkers of Tubular Injury - EGF	Higher	Compared to PBO	estimate < 0 p-one sided=1-p/2 estimate >= 0 p-one sided=p/2
Biomarkers of Tubular Injury: Clusterin	Lower	Compared to PBO	estimate < 0 p-one sided=p/2 estimate >= 0 p-one sided=1-p/2

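### The step-change list for the CMH test of albuminuria category does not match the regression endpoint: it omits macro-to-micro, adds micro-to-macro worsening, and gives no response coding

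*SAP*

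**What the plan says.** SAP 10.1.2 describes the exploratory categorical analysis of ACR in three sentences. The first announces an analysis of gross change in albuminuria status from baseline to Week 16. The second is about improvement: "this will compare the number of subjects in each treatment group who improve from macroalbuminuria at baseline" to micro- or normoalbuminuria, or from micro- to normoalbuminuria. The third names a CMH test stratified by SGLT2i use, pooled CSL346 against placebo. It defines the step change to be tested as "from macroalbuminuria or microalbuminuria to normal albuminuria or microalbuminuria to normal albuminuria OR from microalbuminuria to macroalbuminuria".

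Elsewhere the endpoint is improvement only. Exploratory endpoint 3 in SAP 4.1.4 counts patients "who regress from macroalbuminuria to microalbuminuria or normoalbuminuria, or from microalbuminuria to normoalbuminuria at Week 16 (Visit 10) compared to Baseline", and SAP Table 1 repeats it. Protocol 10.3.7 has the same definition: those "who regress from macroalbuminuria to microalbuminuria or normoalbuminuria, or from microalbuminuria to normoalbuminuria at Week 16 will be counted and compared between treatments". The test named there is Fisher's exact, on pooled CSL346 versus placebo.

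SAP Section 5 opens with "The following represent changes in this SAP from the protocol" and lists two items: the Per-Protocol definition and the removal of VEGF-B. SAP Appendix 16.9 begins "Since treatment comparisons in this study are based on one-sided tests, we need to designate the direction of these tests". Its table has a row for continuous ACR but none for a categorical ACR response.

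**The concern.** The CMH sentence is the only place where the SAP names a test for albuminuria category; it names Fisher's test only for immunogenicity (SAP 11.4.1). Its list is not the endpoint, and it leaves open whether the response is one binary event, an ordered improved/unchanged/worsened response, or two separate tests.

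Programmers working from this sentence could therefore produce different tests, and not all of them point the same way. If the literal list is one binary event, its only common component is a worsening, so an effective drug shows fewer events than placebo. If macro-to-micro was meant but the worsening stays in the same event, the direction is right but the contrast is diluted. With ordered scoring or separate tests there is no sign problem. A choice among these made after unblinding would not be prespecified.

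**Working it through.** **Transitions compared.**

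| Transition | Endpoint (SAP 4.1.4, Table 1; Protocol 10.3.7; second sentence in SAP 10.1.2) | CMH list in SAP 10.1.2 |
|---|---|---|
| macro to micro | yes | absent |
| macro to normo | yes | yes |
| micro to normo | yes | yes, stated twice |
| micro to macro | no | yes |

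**Inputs from the documents.** Entry ACR at least 150 mg/g "from a 24-hour timed urine collection" (Protocol 4.1.1). Category limits 30 and 300 mg/g. SD of change in ln ACR 0.65, a 27% reduction (ln 0.73 = -0.315), 94 completers or 47 per group, one-sided alpha 0.10 (SAP 4.4). The documents give no rate or power for the categorical analysis.

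**The plan's own figure.** SE = 0.65 × √(2/47) = 0.1341. Power = Φ(0.3147/0.1341 − 1.2816) = 85.7%, or 85.4% with the t distribution on 92 df. The stated 85% reproduces, so the SD and effect can be used below.

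**Why the omitted transition dominates.** Let the change in ln ACR be normal with SD 0.65 and mean 0 (placebo) or -0.315 (CSL346). From exactly 150 mg/g, reaching 30 needs ln(30/150) = -1.609, a 5-fold fall:

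- placebo: Φ(−1.609/0.65) = 0.7%
- CSL346: Φ((−1.609 + 0.315)/0.65) = 2.3%

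Any higher baseline makes it rarer. By contrast, from 600 mg/g the chance of falling to micro is 14.3% on placebo and 28.0% on CSL346. From 150 mg/g the chance of rising to macro is 14.3% and 6.1%.

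**Illustration over a baseline distribution (assumed).** Baseline ACR is log-normal with median 600 and log SD 0.9, truncated at 150. For each baseline b, P(normo) = Φ((ln(30/b) − μ)/0.65) and P(macro) = 1 − Φ((ln(300/b) − μ)/0.65), where μ is the mean change. These are integrated over b above or below 300.

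| | Placebo | CSL346 |
|---|---|---|
| macro to micro | 10.90% | 18.83% |
| macro to normo | <0.01% | 0.01% |
| micro to normo | 0.03% | 0.11% |
| micro to macro | 5.61% | 3.11% |
| **Endpoint as defined** (first three) | 10.93% | 18.95% |
| **Literal list, one binary event** (last three) | 5.64% | 3.23% |
| **Macro-to-micro restored, worsening pooled** (all four) | 16.54% | 22.06% |

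Macro-to-micro is over 99% of the defined endpoint. In a group of 47 the literal list expects 47 × 0.0564 = 2.65 placebo events and 47 × 0.0323 = 1.52 CSL346 events.

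**Power.** From 40,000 simulated trials of 47 versus 47 in two nearly equal SGLT2i strata, CMH without continuity correction, one-sided 0.10 in the direction of benefit (level assumed for this test):

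| Response coding | Power |
|---|---|
| Endpoint as defined | 0.43 |
| Literal list, binary | 0.04 |
| Improvement and worsening pooled | 0.27 |
| Row mean scores (+1/0/−1) | 0.47 |

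For the literal list, the statistic passed the same cut-off in the opposite direction in 0.27 of trials.

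**Sensitivity.** For medians 300 to 900 and log SD 0.7 to 1.1, the literal-list proportion is always lower on CSL346: 13.0% to 7.4% at one end, 1.9% to 1.1% at the other. Eligibility uses 24-hour urine but the analysis baseline uses first morning voids. Letting the latter scatter around the former (log SD 0.3 to 0.5, shift 0 to −0.3) leaves the direction unchanged, for example 5.6% to 3.3% and 7.9% to 5.1%.

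**The case against.** The list may be a garbled version of macro to micro or normal, since micro-to-normal appears twice and the correct list stands in the sentence before. That is plausible for the omission. It does not account for the micro-to-macro term, which has its own capitalised OR and still has no coding.

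The third sentence may intend a two-way shift analysis: the paragraph opens with a direction-neutral aim, and Protocol 8.2.2 says transitions will be described. If so, including worsening is deliberate, but a two-way test needs scores or separate tests, and macro-to-micro would still be missing.

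SAP Section 3 puts implementation details in a separate shells document, which may hold the coding. That would lower the practical risk without correcting the SAP.

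Appendix 16.9 covers continuous parameters, and the immunogenicity comparison has no row either. This is fair: the missing row is a gap, not a contradiction.

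The 0.27 wrong-way figure deserves caution. A one-sided test declares nothing in that direction, and the figure rests on very few events. With no treatment difference the uncorrected statistic crosses in each direction in about 0.12 of trials, and with continuity correction 0.27 falls to 0.08. The event proportions are firmer evidence than that figure.

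Finally, even the correct endpoint has power of only 0.43 in the illustration, so this test could never carry much weight.

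**Conclusion.** The concern holds. As written, the CMH list omits macro-to-micro, adds a worsening to an endpoint defined as improvement, and leaves the response uncoded. This is an incorrect stated rule, not only a missing detail.

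How much it matters depends on the coding chosen: reversed sign if the literal list is one binary event, dilution if macro-to-micro is restored with worsening pooled, and no sign problem with ordered scores or separate tests. That regression is nearly all macro-to-micro follows from the entry limit and the plan's SD, with little dependence on the assumed baseline. The exact proportions and powers do depend on that baseline; the power figures also depend on the assumed strata and one-sided 0.10 level.

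The consequence stays within one exploratory test. The improvement comparison, the regression counts and the primary MMRM are unaffected, and no decision rule rests on this result. It should be corrected because the cost is trivial and the coding ought to be fixed before unblinding.

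**What to change.** - In SAP 10.1.2, define the CMH response as exploratory endpoint 3 of SAP 4.1.4 (macro to micro or normo, or micro to normo), and report micro-to-macro progression as a separate count.
- If one two-way test is wanted, score improved, unchanged and worsened as +1, 0 and −1 and name the CMH row-mean-scores statistic, stratified by SGLT2i.
- Add a line to Appendix 16.9 giving the direction of this test.
- In Section 5, record the move from Fisher's exact test to CMH, or state that both will be run.
- While editing, settle the class of a value of exactly 30 mg/g: micro in Protocol 2.3.1, normo in SAP 4.1.3.

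The main change costs one sentence in 10.1.2, one line each in Section 5 and Appendix 16.9, and a derivation flag. It does not touch data collection, sample size or the primary analysis.

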### **4.4 Determination of the Sample Size**

The sample size estimation is based on 2 treatment arms because the primary endpoint analyses will compare CSL346 (8 mg/kg and 16 mg/kg combined) with placebo. The planned sample size is 100 subjects with 50 subjects receiving CSL346 (8 mg/kg, n = 25 and 16 mg/kg, n = 25) and 50 subjects receiving placebo. Assuming a SD of 0.65 for the change from Baseline to Week 16 (Visit 10) in ACR following natural log transformation, a sample size of 94 subjects is estimated to provide 85% power to detect a 27% reduction in the geometric mean ACR for CSL346 versus placebo, i.e.  $\ln(1 - 0.27) = -0.315$  on the natural log scale, using a one-sided  $\alpha = 0.10$ . For this study, statistical significance will be achieved with an observed treatment effect of  $-0.173$  on the natural log scale, or approximately  $-16\%$  when expressed as a percent difference in treatments, depending on the observed variability. The planned total sample size of 100 subjects accounts for an assumed 6% drop-out rate. The actual early discontinuation rate will be assessed throughout the study and up to 124 subjects may be randomized if necessary, to target 94 completed subjects (subjects who received all doses and completed the Week 16 ACR assessment).

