### 10.1.2 Primary Efficacy Analysis

The primary analysis is a mixed effects model, repeated measures (MMRM) analysis of the change from baseline through 24 weeks of log ACR, with the primary treatment comparison at Week 16 (Visit 10). The model will include treatment (at 3 levels: 8 mg/kg CSL346, 16 mg/kg CSL346, and placebo), baseline log ACR, the stratification variable related to the concomitant use of SGLT2i, visit (as a categorical factor), and interactions between visit and each of the other model terms as factors. The primary comparison of interest will be calculated using a contrast of  $0.5 (8 \text{ mg/kg CSL346} + 16 \text{ mg/kg CSL346}) - \text{Placebo}$ . Please see [Section 16.1](#) for the corresponding SAS Code for the MMRM model. Because this is an early development study and the first study in subjects with T2DM, the one-sided alpha level to be employed for this test is 0.10. Estimated treatment effect of individual CSL346 dose levels versus placebo will also be summarized. The treatment comparisons will be expressed as a percent difference in treatments, calculated as  $100\% \times (\text{geometric mean ratio of the treatment comparison} - 1)$ . The covariance matrix structure to be employed in the primary analysis will be an unstructured pattern. In the event of model convergence issue, a Toeplitz heterogeneous structure will be employed. If the model still fails to converge an autoregressive structure ARH(1) will be assumed.

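### The exploratory albuminuria-category test is stratified by SGLT2i alone and ignores baseline ACR, which costs a few points of power and leaves the result open to chance baseline imbalance

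*SAP*

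**What the plan says.** SAP 10.1.2 introduces the analysis in these terms: "An exploratory analysis of the primary endpoint of ACR will be a categorical analysis of the number of subjects" whose albuminuria status changes between baseline and Week 16. It counts subjects "who improve from macroalbuminuria at baseline (ACR >300 mg/g [33.9 mg/mmol]) regressing to microalbuminuria" or normoalbuminuria, and subjects moving from microalbuminuria to normoalbuminuria. For the test, a "Cochran-Mantel-Haenszel test stratified for SGLT2i will be employed to compare subjects receiving CSL346 versus placebo". The parenthesis in that sentence, which defines a step change, also lists movement from microalbuminuria up to macroalbuminuria.

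Protocol 10.3.7 counts regressions only. They "will be counted and compared between treatments using Fisher's Exact Test", with no strata. SAP Section 5, which lists departures from the protocol, does not mention the move from Fisher to CMH.

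The primary MMRM in the same SAP section includes "baseline log ACR, the stratification variable related to the concomitant use of SGLT2i". Its baseline ACR is derived from six first-morning-void (FMV) samples (SAP 8.2.3). SAP 9.3 already defines three baseline ACR bands: 30 to 300, above 300 to 1000, and above 1000 mg/g. Randomization is stratified by SGLT2 inhibitor use only (Protocol 6.2).

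**The concern.** Regression means crossing a fixed threshold, so a subject's distance from the line at baseline is the main determinant of the outcome. SGLT2i use is not part of the threshold definition, yet it is the only stratification factor. Neither the randomization nor the test balances or adjusts for the number of subjects who start just above 300 mg/g.

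Two things are at stake. Variation that a known, already derived covariate could explain is left in the comparison, which costs power. In addition, in a trial of about 100 subjects, a chance excess of near-threshold subjects in one arm can make regression look more or less frequent under CSL346. That result would be read beside the primary estimate.

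**Working it through.** **1. The plan's own figure.** The only power statement in the documents concerns the primary endpoint (SAP 4.4): "a sample size of 94 subjects is estimated to provide 85% power to detect a 27% reduction in the geometric mean ACR". Its inputs are an SD of 0.65 for the log change, an effect of −0.315 and one-sided 0.10.
- SE of the difference at 47 per arm = 0.65 × √(2/47) = 0.1341.
- Power = Φ(0.315/0.1341 − 1.2816) = Φ(1.068) = 85.7%.
- Critical effect = 1.2816 × 0.1341 = 0.172, or 1.291 × 0.1341 = 0.173 with the t quantile on 92 df.

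The plan's 85% and −0.173 are reproduced. No power, event rate or alpha is stated for the category test.

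**2. How strongly baseline decides the outcome.** The fall needed is 1 − threshold/baseline. If the change in ln ACR is normal with SD 0.65, whatever the baseline, the chance of regressing is Φ((ln(threshold/baseline) − effect)/0.65). The effect is 0 on placebo and −0.315 on CSL346.

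| Baseline → threshold (mg/g) | Fall needed | Placebo | CSL346 |
|---|---|---|---|
| 320 → 300 | 6% | 46% | 65% |
| 600 → 300 | 50% | 14% | 28% |
| 1000 → 300 | 70% | 3.2% | 8.6% |
| 1500 → 300 | 80% | 0.7% | 2.3% |
| 150 → 30 | 80% | 0.7% | 2.3% |
| 300 → 30 | 90% | 0.02% | 0.1% |

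On placebo the chance runs from nearly one half to nearly zero with baseline alone. It is also not monotone: it drops almost to zero just below 300 mg/g. A model therefore needs the baseline category as well as log ACR.

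**3. What ignoring it costs.** This part needs assumptions that the documents do not supply:
- Baseline ACR is lognormal and truncated at 150 mg/g. That floor comes from "Urinary ACR ≥ 150 mg/g (16.95 mg/mmol) from a 24-hour timed urine collection".
- SGLT2i use is 50:50 and not prognostic.
- The primary effect and one-sided 0.10 are carried over to this test.
- The outcome is regression only.

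There were 47 subjects per arm and 20,000 simulated trials per scenario. Entries are power in %, with type I error in % in brackets.

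| Median, log-SD | CMH by SGLT2i | CMH + ACR bands | Logistic score test, log ACR | Gain at equal size: bands / log ACR |
|---|---|---|---|---|
| 300, 0.6 | 43.0 (10.1) | 47.8 (9.9) | 50.8 (10.5) | 5.6 / 7.1 |
| 300, 0.9 | 42.8 (10.5) | 46.8 (10.3) | 50.5 (11.3) | 4.3 / 5.8 |
| 400, 0.9 | 43.2 (10.3) | 46.1 (10.1) | 50.5 (11.2) | 3.1 / 5.2 |
| 600, 0.6 | 49.5 (10.1) | 51.4 (9.9) | 55.8 (10.8) | 2.1 / 4.8 |
| 600, 0.9 | 43.2 (10.6) | 45.5 (10.4) | 49.7 (11.3) | 2.5 / 5.0 |
| 800, 0.9 | 40.6 (10.6) | 42.8 (10.4) | 47.3 (11.4) | 2.9 / 5.3 |
| 800, 1.2 | 37.7 (10.8) | 39.9 (10.3) | 44.3 (11.4) | 4.3 / 6.1 |
| 1000, 0.9 | 39.1 (11.1) | 40.3 (10.5) | 45.0 (12.1) | 3.8 / 5.1 |

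The nominal gains here are 1.2 to 4.8 points for the bands and 5.9 to 7.8 for log ACR. Part of the latter reflects a slightly liberal score test. A further set of runs gave about 5 to 9 points nominally and 3 to 8 at equal size for log ACR. A lightly penalised model held its size (0.102 to 0.106) and still gained 4 to 5 points, for example 45.1% to 50.5% and 37.6% to 42.5%.

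**4. Chance imbalance.** With no treatment effect, the CSL346 arm has over 10 percentage points more subjects at 300 to 600 mg/g in 12 to 17% of simulated trials. In those trials the SGLT2i-stratified CMH declares benefit 23 to 25% of the time. With the opposite imbalance it does so 2 to 4% of the time. The adjusted test stays at 11 to 13% and 9 to 10%.

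**The case against.** The analysis is labelled exploratory and carries no power claim or decision rule. Stratifying by the sole randomization factor is conventional. The baseline-adjusted question on the same measurements is already answered by the primary MMRM, and power is poor either way. All of this stands and keeps the point minor.

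The outcome that the CMH would test is itself unclear. If improve/same/worsen is scored, CMH power was 42 to 50% against 45 to 52% for the adjusted regression test, a gap of only about 1 to 4 points. A literal any-change reading gave 22 to 32%. So the loss depends on a definition the SAP has not fixed. This also stands.

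The truncation at 150 mg/g borrows an entry floor from a 24-hour collection at screening, whereas the analysis baseline comes from FMV samples with no such floor. The size of the gain therefore rests on assumption; its direction did not change in any regression-only scenario.

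Events are few. In simulation there were 11 to 17 regressions per trial, and in 89 to 98% of trials no microalbuminuric subject regressed. A baseline-category term is then separated in ordinary logistic regression. This rules out an unpenalised fit, but not adjustment.

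A reader might infer that the planned CMH is invalid. It is not. Averaged over randomizations its type I error is close to nominal (10.1 to 11.1% in the table), and imbalance is part of that error. The case for adjustment rests on precision and on how the one realised trial is read.

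**Conclusion.** The point holds as a minor improvement. Baseline ACR strongly determines who can regress, and the category test ignores it in both documents. Under the assumed baselines, one-sided 0.10 and a regression-only outcome, the cost is roughly 3 to 8 points of power at equal type I error against continuous log-ACR adjustment, and about 1 to 5 points nominally against adding the SAP's bands. It is less if worsening is scored. At one-sided 0.025 and equal size, the gain from log ACR was about 2 to 5 points.

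A reader might take a figure such as 6 to 8 points as a fixed property of the plan. The documents do not support that. They give no baseline ACR distribution and no alpha for this test, SAP 16.9 does not list it, and such a figure includes some size inflation. Nor does the point touch the primary analysis, which already adjusts for baseline log ACR.

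**What to change.** In SAP 10.1.2:
- Define the tested outcome as regression (yes/no), and report micro-to-macro worsening separately.
- Test it with a penalised-likelihood (Firth) logistic regression on treatment, SGLT2i, baseline category (macro/micro) and baseline log ACR. More simply, add the three ACR bands as CMH strata beside SGLT2i.
- If bands are used, derive them from the FMV baseline that defines the categories. SAP 9.1 refers to 24-hour urine for the same cut-points.
- State the alpha and direction of the test, and keep the SGLT2i-stratified CMH as supportive.
- List the change from Fisher's test in SAP Section 5.

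The cost is a few sentences and one model, with no new data. The odds ratio becomes conditional on baseline, and an unpenalised score test would be slightly liberal. The change should be made before unblinding for the Week 16 interim analysis; if made later, the adjusted result should be labelled post hoc.
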